2.2.1 Subgroup of interest

The following subgroups will be used for the primary variable:

- Subgroups:
 - Risk for COVID-19 disease progression (“high-risk”, “not at high-risk”) – as per protocol
 - Risk for COVID-19 disease progression (“high-risk”, “not at high-risk”) - as per FDA updated definition on May 19, 2021
 - Geographical region (North America, Europe, Africa, Asia)
 - Gender (Male, Female)
 - Age (<55 years, 55-<65 and \geq 65 years)
 - Mutation type (Wild type; Alpha B.1.1.7; Beta B.1.351; Gamma P.1; Delta B.1.617.2; Lambda C.37; Other)*, if available
 - Baseline \log_{10} SARS-CoV-2 viral load (\log_{10} SARS-CoV-2 viral load < 6 , \log_{10} SARS-CoV-2 viral load ≥ 6)
 - SARS-CoV-2 antibodies at baseline (No, Yes)
 - Baseline severity of COVID-19 (mild, moderate)

* List of mutation types may be updated if new variants of concern are detected during the study.

Mutation type data will only be partially available at the time of part A primary analysis, therefore this subgroup will be analyzed at the time of final lock i.e., day 91 analyses only.

Subgroups may need to be combined if there is not a sufficient number of patients (e.g. at least 10%) in a respective subgroup. Regions will only be combined if models fail to converge, whether or not having less than 10%.

For tables presenting results from statistical models, the treatment effects in the subgroup will be derived using an additional covariate as a fixed effect and the appropriate interaction terms in the model, if necessary.

2.3 Patient disposition, demographics and other baseline characteristics

2.3.1 Patient disposition

The number of patients in each analysis set will be presented overall for the SCR and by treatment group for the RAN.

The number of patients in the FAS will be summarized by region, country, center and treatment group.

The number and percentage of patients in the SCR who were randomized or discontinued study prior to randomization, including the reason for discontinuation will be presented overall.

The number and percentage of patients in the RAN who completed or discontinued study, including the reason for discontinuation will be presented overall and by treatment group.

The frequency (%) of patients with CSR reportable protocol deviations will be presented for the RAN. Other criteria leading to exclusion from analysis sets will be listed.

These summaries will be produced independently for Part A and Part B.

2.3.2 Background and demographic characteristics

Demographic and other baseline data including disease characteristics will be listed and summarized descriptively by treatment arm for the FAS and SS (if different from the FAS).

Demographics listed below will be summarized:

- Age (years)
- Gender (Male, Female)
- Race (White, Black or African American, Asian, Native Hawaiian or Other Pacific Islander, American Indian or Alaska Native, Multiple, Unknown, Not reported)
- Ethnicity (Hispanic, Non-hispanic)
- Age group (<25 years, 25-<45 years, 45-<65 and \geq 65 years)
- Geographical region (North America, Europe, Africa, Asia)

The following baseline characteristics will be summarized:

- Body weight (kg)
- BMI (kg/m^2), calculated as weight in kg divided by (height in m) 2
- BMI group (<18.5 kg/m^2 , 18.5-<25 kg/m^2 , 25-<35 kg/m^2 , \geq 35 kg/m^2)
- Risk for COVID-19 disease progression (“high-risk”, “not at high-risk”) – as per protocol
- Risk for COVID-19 disease progression (“high-risk”, “not at high-risk”) – as per FDA updated definition on May 19, 2021
- Chronic kidney disease (No, Yes)
- Diabetes mellitus (No, Yes)
- Immunosuppressive disease (No, Yes)
- Currently receiving immunosuppressive treatment (No, Yes)
- \geq 65 years of age (No, Yes)
- \geq 55 years of age and cardiovascular disease, or hypertension, or chronic obstructive pulmonary disease / other chronic respiratory disease (No, Yes)
- Baseline ADA status (ADA+, ADA-)*
- Baseline \log_{10} SARS-CoV-2 viral load (copies per mL)
- Baseline \log_{10} SARS-CoV-2 viral load (\log_{10} SARS-CoV-2 viral load $<$ 6, \log_{10} SARS-CoV-2 viral load \geq 6)

- Mutation type (Wild type; Alpha B.1.1.7; Beta B.1.351; Gamma P.1; Delta B.1.617.2; Lambda C.37; Other)*, if available
- SARS-CoV-2 antibodies as baseline (No, Yes)
- Baseline severity of COVID-19 (mild, moderate, severe (if appears)). Details on definition are included in [Section 5.2](#).

* ADA samples will not be analyzed for Placebo patients, therefore ADA status will be missing for Placebo patients.

2.3.3 Medical history/current medical condition

Medical history will be coded with the Medical Dictionary for Regulatory Activities terminology (MedDRA) using the most recent version at the time of database lock. History/conditions, including pre-specified events, will be summarized for the FAS by primary system organ class, high level term (HLT), and preferred term.

2.4 Treatments (study treatment, rescue medication, concomitant therapies, compliance)

2.4.1 Study treatment / compliance

The analysis of study treatment will be based on the SS. All study treatment summaries will be presented by treatment arm.

The number and percentage of patients with discontinuation of study medication, if applicable, will be summarized by reason for discontinuation.

2.4.2 Prior, concomitant and rescue therapies

Prior, concomitant, and rescue therapies will be summarized based on the FAS.

Prior medications are defined as medications started prior to start of study drug and discontinued prior to start of study drug.

Concomitant medications are defined as medications starting prior to start of study drug and are ongoing at Day 1, or started after/at Day 1.

All medications will be summarized separately for prior and concomitant medications by anatomical main group (the 1st level of the ATC codes), ATC code (4th level or if not available next higher level), preferred term and treatment group.

A patient with multiple medications of the same anatomical main group, ATC class or preferred term will only be counted once towards the specific anatomical main group, ATC class or preferred term.

Number and percentage of patients who received COVID-19 vaccinations will be presented along with the number of doses received and time since most recent dose (<15 days, 15-<180 days, >=180 days).

In addition, the number and percentage of patients who received concomitant medications related to COVID-19 will be summarized by category (anti-virals, immune-

modulating/immunosuppressant, other) and by preferred term, separately for concomitant medications initiated before study medication and concomitant medications initiated after study medication.

Rules for imputing incomplete dates are described in [Section 5.1.3](#).

2.5 Analysis of the primary objective

Part A

The primary analysis in Part A is conducted on the data cut performed after the last enrolled Part A patient completes Day 29 visit or discontinues prematurely.

Part B

The primary analysis in Part B is conducted on the data cut performed after the last enrolled Part B patient completes Day 91 visit.

An outline of the protocol-specified analysis of Part B is provided in the SAP. Further details will be provided in a SAP amendment before FPFV of Part B.

2.5.1 Primary endpoint

Part A

In Part A, the primary variable for the study is a virologic endpoint defined as time-weighted change from baseline to Day 3, 5, and 8 (2, 4, and 7 days after dosing, respectively) in \log_{10} SARS-CoV-2 viral load in nasopharyngeal swabs.

To calculate the time-weighted change from in \log_{10} SARS-CoV-2 viral load through Day 8 for each patient, the equation below is used:

$$\frac{\sum_{i=a}^{b-1} \{0.5(Y_i + Y_{i+1})(t_{i+1} - t_i)\}}{t_b - t_a}$$

where Y_i is the change from baseline in \log_{10} SARS-CoV-2 viral load at Visit i , t_i is the time at the Visit i (the actual study day), a is the baseline assessment at Day 1, and b is the last assessment at or prior to Day 8. Viral load values below the lower limit of quantification (LLOQ) will be imputed as 0.5*value of the LLOQ. Viral load values above the upper limit of quantification (ULOQ) will be imputed as value of the ULOQ.

The primary estimand definition is as follows:

- **Population:** defined through appropriate inclusion/exclusion criteria to reflect the targeted population, ambulatory adult patients with newly symptomatic COVID19 with onset of symptoms within 7 days prior to dosing and with a positive rapid antigen test on the day of dosing
- **Treatment of interest:** the randomized treatment (ensovibep 75 mg, 225 mg, 600 mg, or placebo) added to concomitant symptomatic/preventive treatments, including symptomatic therapies (e.g., antipyretics/analgesics such as ibuprofen, paracetamol/acetaminophen, aspirin) and anticoagulants (e.g., heparin), used for mild-to-moderate COVID-19

- **Endpoint:** time-weighted change from baseline (measured at Day 3, Day 5, and Day 8) in \log_{10} SARS-CoV-2 viral load in nasopharyngeal swabs through Day 8
- **Handling of intercurrent event(s):** A combination of treatment policy and composite strategy will be used to handle the intercurrent events. A treatment policy strategy will be used to handle (1) post-treatment initiation of all antivirals (including convalescent serum, antiviral antibodies, and antiviral small molecules), immunomodulating medications; and, (2) post-treatment increase in dose of immunosuppressive medications, for the treatment or management of COVID-19. A composite strategy will be used to handle (3) death from any cause and (4) COVID-19 related hospitalization.
- **Summary measure:** adjusted mean time-weighted change from baseline (measured at Day 3, Day 5, and Day 8) in \log_{10} SARS-CoV-2 viral load in nasopharyngeal swabs between the ensovibep 75 mg, 225 mg, and 600 mg compared to placebo arms.

Part B

In Part B, the primary variable is a clinical efficacy endpoint defined as any of the following up to Day 29:

- Hospitalizations (≥ 24 hours of acute care) related to COVID-19; OR,
- Emergency room visits related to COVID-19; OR,
- Death from any cause.

If a patient experiences more than one of the events, the first event to occur will be counted towards the clinical efficacy endpoint and the date at which the first event occurred will be used as time date at which the clinical efficacy endpoint was achieved.

The primary estimand definition is as follows:

1. **Population:** defined through appropriate inclusion/exclusion criteria to reflect the targeted population, ambulatory adult patients with newly symptomatic COVID-19 with onset of symptoms within 7 days prior to dosing and with a positive rapid antigen test on the day of dosing
2. **Treatment of interest:** the randomized treatment (ensovibep [dose selected from Part A] or placebo) added to concomitant symptomatic/preventive treatments, including symptomatic therapies (e.g., antipyretics/analgesics such as ibuprofen, paracetamol/acetaminophen, aspirin) and anticoagulants (e.g., heparin), used for mild-to-moderate COVID-19
3. **Endpoint:** the binary response of patients experiencing hospitalizations (≥ 24 hours of acute care) and/or emergency room visits related to COVID-19 or death from any cause up to Day 29 (Yes/No)
4. **Handling of intercurrent event(s):** A treatment policy strategy will be used to handle (1) post-treatment initiation of all antivirals (including convalescent serum, antiviral antibodies, and antiviral small molecules), immunomodulating medications; and, (2) post-treatment increase in dose of immunosuppressive medications, for the treatment or management of COVID-19.

5. **Summary measure:** difference in proportions of patients experiencing hospitalizations (\geq 24 hours of acute care) and/or emergency room visits related to COVID-19 or death from any cause up to Day 29 of ensovibep (dose selected from Part A) compared to placebo

2.5.2 Statistical hypothesis, model, and method of analysis

Part A

The primary objective of this Part is to demonstrate a dose-response effect of ensovibep compared to placebo defined as time-weighted change from baseline in \log_{10} SARS-CoV-2 viral load through Day 8. The MCP-Mod methodology ([Bretz et al 2005](#), [Pinheiro et al 2014](#), [Qualification Opinion on MCP-Mod EMA 2014](#), [FDA endorsement 2016](#)) to address this objective and confirm an overall dose-response signal, characterize the dose response efficacy relationship across the dose range of ensovibep, and estimate the smallest dose(s) that corresponds to the clinically relevant effect over placebo with regards to time-weighted change from baseline in \log_{10} SARS-CoV-2 viral load through Day 8.

The null hypothesis of a constant dose-response curve for the time-weighted change from baseline in \log_{10} SARS-CoV-2 viral load through Day 8 will be tested at a one-sided 10% alpha level against the alternative hypothesis of a non-constant dose-response curve using the MCP-Mod methodology.

Generalized MCP-Mod ([Pinheiro et al 2014](#)) will be employed in a three-step approach in the steps is given below:

- Conventional step – covariate-adjusted mean response for each dose

The data are analyzed using analysis of covariance (ANCOVA) to obtain covariate adjusted treatment effects and corresponding variance covariance matrix. The ANCOVA will adjust for baseline \log_{10} SARS-CoV-2 viral load, treatment group, baseline risk of progression to severe COVID-19 and/or hospitalization (“high risk” vs. “not at high risk”) and presence of SARS-CoV-2 antibodies (Yes vs. No) and Geographical region (North America, Europe, Africa, Asia) as covariates.

The estimated treatment difference and the associated 95% confidence intervals will be presented for the treatment contrast of each dose versus placebo.

- Proof-of-concept step – multiple contrast tests

[figure not shown]
The null hypothesis of flat dose-response relationship as compared to placebo for the primary efficacy endpoint will be tested at a significance level of one-sided 10% against the alternative hypothesis of a non-constant dose-response curve using a multiple contrast test as described in the Generalized MCP-Mod methodology ([Pinheiro et al 2014](#)). The contrast test statistic is a linear combination of the optimal contrast coefficients corresponding to the candidate dose-response curve with the adjusted mean responses at each individual dose obtained from Step 1.

The contrast coefficients will be chosen to maximize the power to detect pre-specified candidate models ([Pinheiro et al 2014](#)). For that purpose, the E_{max} dose-response shape ($E_0 + E_{max} * d/(d + ED_{50})$) with three shapes of $ED_{50} = 8, 40, 180$ and the sigmoid

E_{max} dose-response shape ($E_0 + E_{max} * d^h / (d^h + ED_{50}^h)$) with two shapes of $(ED_{50}, h) = (120, 4)$ and $(450, 3)$ will be used where E_0 is the expected placebo effect, E_{max} is the maximum change in effect over placebo, ED_{50} is the dose at which 50% of E_{max} is achieved, and h is Hill parameter (Figure 2-1).

The global test decision is based on the maximum of the contrast test statistics. A critical value q controlling the type I error rate can be derived from the fact that the contrast test statistics approximately follow a multivariate normal distribution and that their maximum follows the distribution of the maximum of a multivariate normal distribution. If the maximum contrast test statistic exceeds the critical value q , the overall null hypothesis of a constant dose-response curve is rejected and one proceeds to characterize the dose response efficacy relationship and estimate the optimum dose(s) that corresponds to the clinically relevant effect over placebo.

Figure 2-1 Candidate models for ensovibep dose

For each candidate dose-response curve, the test statistics and corresponding adjusted p-values will be presented.

- Dose-finding step – dose-response model fitting

A bootstrap sample (from a normal distribution with LSMeans and corresponding covariance matrix from an ANCOVA) is used to fit the non-linear dose-response functions and obtain parameter estimates for each model. Bootstrap model averaging based on AIC over all significant model families considered in the analysis will be used to estimate the final dose-response shape, to calculate the optimum dose(s) by substituting the values for the placebo-adjusted dose response in the model and solving for dose, and to derive the 95% confidence intervals. Bootstrap simulation will be performed using the multivariate normal distribution of the adjusted estimates of the population means for each dose and generalized least-squares fitting of the resulting

simulated values (Pinheiro et al 2014). The dose-response estimate will be the median across the bootstrap model predictions and 95% confidence intervals based on bootstrap quantiles.

The dose-response curve estimate with the model-based two-sided 95% confidence interval will be presented graphically. In addition, the plot will include the mean responses from the ANCOVA and the associated 95% confidence intervals for each of the studied dose groups.

Further details on the MCP-mod are described in [Section 5.7.1](#).

The target dose(s) will be estimated from MCP-mod for a delta of 0.36 and 0.68 based on the estimated dose-response curve (median of bootstrap estimates). The target dose is the smallest dose among the investigated doses which reaches the effect of delta..

The target dose(s) suggested by MCP-Mod based on viral endpoint serves as an important consideration in dose selection. However, the final dose selection for Part B will be determined based on the following

- Efficacy of doses based on rate of occurrence of hospitalizations (\geq 24 hours of acute care) and/or emergency room visits related to COVID 19 or death from any cause up to day 29, FDA/modified FDA symptom score; AND,
- Safety endpoints including [REDACTED] AESIs, AEs, and SAEs.

Part B

The primary objective of this Part is to demonstrate superiority of ensovibep, compared to placebo, in reducing the occurrence of hospitalizations (\geq 24 hours of acute care) and/or emergency room visits related to COVID 19 or death from any cause up to Day 29.

The cumulative proportion of experiencing hospitalizations (\geq 24 hours of acute care) and/or emergency room visits related to COVID 19 or death from any cause up to Day 29 will be estimated for each randomized group using Kaplan-Meier methods to take account of losses to follow-up.

The difference between randomized groups in the estimated log cumulative proportion will be calculated and the variance for this difference will be obtained using Greenwood's formula. Two-sided 95% confidence intervals (adjusted for an interim analysis) and associated p-value for the test of no difference between groups will then be obtained.

The hazard ratios for these comparisons for the occurrence of hospitalizations (\geq 24 hours of acute care) and/or emergency room visits related to COVID 19 or death from any cause and their corresponding 95% confidence intervals will be computed using a stratified Cox proportional hazards regression model, stratified by baseline risk of progression to severe COVID-19 and/or hospitalization ("high risk" vs. "not at high risk").

Time to hospitalizations (\geq 24 hours of acute care) and/or emergency room visits related to COVID 19 or death from any cause will be presented graphically with a Kaplan-Meier plot.

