## 4 Rationale

### 4.1 Rationale for study design

The rationale for the various study design aspects of the study is presented in [Table 4-1](#).

**Table 4-1** Rationale for study design

Study Design Aspect	Rationale
Part A primary endpoint selection of time-weighted change from baseline (measured at Day 1 (pre-dose), Day 3, Day 5, and Day 8) in $\log_{10}$ SARS-	To assess antiviral activity of the compound, anticipated to be the most informative parameter for dose selection. It is expected

Study Design Aspect	Rationale
CoV-2 viral load in nasopharyngeal swabs through Day 8.	that in the first week after symptom onset the effect of ensovibep is most prominent.
Part B primary endpoint selection of proportion of patients with hospitalizations ( $\geq$ 24 hours of acute care) and/or emergency room visits related to COVID-19 or death from any cause up to Day 29.	To assess a clinically meaningful endpoint as requested by regulatory authorities for up to 4 weeks after treatment.
Duration of long-term follow-up at Day 91.	To evaluate long-term safety and track for long-COVID symptoms.
Parallel design, 4 treatment arms in Part A.	To evaluate different dose levels of ensovibep versus placebo and determine the optimal efficacious and safe dose.
Parallel design, 2 treatment arms in Part B.	To confirm efficacy and safety of the optimal dose identified based on data from Part A versus placebo.
Randomization and placebo arm.	Randomization and the inclusion of a control arm are essential to control unintended introduction of bias into the study results necessary to establish the safety and efficacy of ensovibep in COVID-19. A placebo arm is planned for comparison as no antiviral therapy is approved for treatment of ambulatory COVID-19 patients.
Blinding.	The double-blinded design is important, to make objective assessments of the pharmacological effect of the study treatment and to minimize the effect of assessment bias.
Single-dose study.	Based on the predicted serum half-life of two to three weeks in humans, a single systemic dose regimen is proposed for treatment of COVID-19.
Phase 2 and Phase 3 study in the same protocol.	To improve the operational efficiency between identifying a safe and efficacious dose in the dose-ranging study Part A and the initiation of the Phase 3 confirmatory study in Part B.
Interim analysis in Part B.	To allow for early stopping for efficacy using appropriate alpha spending.

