2.7.2.2 COVID-19 symptoms

The cumulative proportion of achieving sustained clinical recovery up to Day 29 will be estimated for each treatment group using Kaplan-Meier methods to take account of losses to follow-up.

The treatment differences in the estimated log cumulative proportion will be calculated and the variance for this difference will be obtained using Greenwood's formula. Two-sided 95% confidence intervals and associated p-value for the test of no difference between groups will then be obtained.

Number and percentage of patients with and without event will be tabulated along with the time at risk, event rates and corresponding 95%CI. Additionally, a Kaplan-Meier plot will be presented.

Time to sustained clinical recovery will be presented graphically with a Kaplan-Meier plot. A Cox proportional hazards model will be used, stratified by baseline risk of progression to severe COVID-19 and/or hospitalization ("high risk" vs. "not at high risk"). The model will include treatment, presence of SARS-CoV-2 antibodies (Yes vs. No), Geographical region (North America, Europe, Africa, Asia). Time of onset of COVID-19 symptoms (days relative to Day 1) will also be evaluated as a predictor in the model.

As a descriptive summary, shift tables presenting shifts from baseline to post-baseline will be provided for each question by selected visits (Day 3, Day 8, Day 15, and Day 29) and treatment group. Question on return to usual health and return to usual activities will be summarized for post-baseline visits only. Further a descriptive summary of the COVID-19 symptom score will be provided by scheduled timepoint. The symptom score ranges from 0 to 24 and includes eight domains (cough, breathlessness, feeling hot, fatigue, body pain, sore throat, chills and headache), each is graded on a scale of 0 (no symptoms) to 3 (severe symptoms).

Prior to database lock for primary analyses it was detected that due to non-compliance at sites some patients did not complete the COVID-19 symptom questionnaire prior to start of infusion. These patients do not have valid baseline data for COVID-19 symptom questionnaire. Therefore the following supportive analysis will be performed:

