3.1 Primary endpoint(s)

Part A

In Documentation for the EUA for emergency use of casirivimab and imdevimab, issued 21 Nov 2020, it is shown that the treatment effect in time-weighted change from baseline (Day 1) to Day 8 of \log_{10} SARS-CoV-2 viral load in nasopharyngeal swabs was -0.36 for the overall population and -0.68 for the subgroup of patients with at least 10^7 copies at baseline and the estimated standard deviation was between 1.0 and 1.2.

Assuming the published evidence to be predictive over 8 days, a sample size of at least 100 patients per treatment group, for a total of 400 patients, would have at least 80% power (minimum power over the considered candidate shapes) with a one-sided Type I error rate of 0.10 to detect a dose-response trend versus placebo using MCP-Mod to select the smallest dose for consideration in the decision to move into Part B.

The power calculation given the range of operating characteristics (treatment effect: -0.36, -0.68, and standard deviation: 1, 1.1, 1.2) were performed based on MCP-Mod in R (Pinheiro 2006) and are presented in [Table 3.1-1](#).

Table 3.1-1 Power for Part A given a range of operating characteristics given 400 patients, 100 patients in each arm and a one sided significance level of 10%

Treatment Effect	Standard Deviation	Power (%)
-0.36	1	90.03
	1.1	85.25
	1.2	80.25
-0.68	1	99.98
	1.1	99.92
	1.2	99.73

Part B

Assuming the proportion of patients achieving the composite endpoint (of hospitalizations (\geq 24 hours of acute care) and/or emergency room visits, related to COVID-19, or death from any cause) up to Day 29 is 6.5% based on [Gottlieb et al \(2021\)](#) in the placebo group and 50% reduction with to 3.25%, a sample size of 1717 patients 1:1 randomized to two treatment groups provides at least 90% power that the primary analysis will be statistically significant using a two-sided log rank test with 5% significance level assuming that the survival rates are exponential. These results assume that the group sequential design has one interim analysis for

stopping the trial early for efficacy after 50% of patients complete Day 29 visit (two total analysis including final analysis) and the O'Brien-Fleming spending function is used to determine the efficacy test boundary.

Given possible enrichment for more severe COVID-19 cases, a range of operating characteristics were evaluated and presented in [Table 3.1-2](#).

Sample size calculations are performed in nQuery 8.4.1.0.

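### The Part A primary ANCOVA does not adjust for days since symptom onset; adding it is an optional, low-cost gain in precision, not the correction of an error

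*SAP*

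**What the plan says.** SAP 2.5.2 lists the covariates of the Part A primary ANCOVA: baseline log10 viral load, treatment group, baseline risk of progression, "presence of SARS-CoV-2 antibodies (Yes vs. No) and Geographical region". The model equation in SAP 5.7.1 repeats the list. Time since symptom onset is in neither place. It is also absent from:

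- the supportive MMRM (SAP 2.5.5 and 5.7.1);
- the imputation models for the jump-to-reference analysis (SAP 5.7.1);
- the subgroup list (SAP 2.2.1);
- the baseline characteristics to be tabulated (SAP 2.3.2).

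The variable appears once in the analysis plan, in the Cox model for time to sustained recovery (SAP 2.7.2.2): "Time of onset of COVID-19 symptoms (days relative to Day 1) will also be evaluated as a predictor in the model".

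Three places in the protocol bear on the choice. Section 5.1 admits patients whose symptoms began no more than 7 days before dosing. Section 1.1 cites kinetic studies in which replication in the pharynx is heavy shortly before and soon after symptoms start. Section 12.4.2 leaves it to the SAP to name further covariates, so adding one needs no protocol amendment. Neither document gives a reason for leaving onset time out.

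**The concern.** The primary endpoint is the time-weighted change in log10 viral load from Day 1 to Day 8. Patients may enter anywhere from the day of onset to a week later, a spread about as wide as the measurement window. If viral load follows a course tied to onset, as Protocol 1.1 suggests, a patient's expected change over the next week depends partly on where on that course treatment begins. One baseline swab gives a level, and a yes/no antibody result is a coarse marker of timing. Days since onset might therefore explain some outcome variance that the listed covariates leave over.

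What is at stake is precision only. The ANCOVA means and their covariance matrix feed both the contrast tests and the bootstrap dose-response curve, so a smaller residual variance would carry through to dose finding. Randomisation is stratified by risk alone. A chance imbalance in onset time between arms would thus be neither adjusted for nor shown in the planned baseline table.

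**Working it through.** **Inputs.** From SAP 3.1: "a sample size of at least 100 patients per treatment group, for a total of 400 patients"; an effect that "was -0.36 for the overall population and -0.68 for the subgroup" with high baseline load; and "the estimated standard deviation was between 1.0 and 1.2". From SAP 2.5.2: the flat-curve null "will be tested at a one-sided 10% alpha level against the alternative hypothesis of a non-constant dose-response curve". Doses are 0, 75, 225 and 600 mg with equal allocation. The candidate shapes are Emax with ED50 = 8, 40, 180 and sigmoid Emax with (ED50, h) = (120, 4), (450, 3).

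**Step 1: reproduce the plan's power.** Each shape f is scaled so that its difference from placebo at 600 mg equals 0.36 (a reduction counted as positive). With equal arms, the optimal contrast for a shape is c = (f − mean of f) / ‖f − mean of f‖. The test statistic is T = c′ȳ / (SD/√100), and its noncentrality under a true shape g is c′g / (SD/√100). The critical value for the largest of the five statistics, from 1,000,000 simulations with 396 degrees of freedom, is 1.688. Power is the chance that the largest statistic exceeds it, and the minimum is taken over the five true shapes.

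| Effect | SD | Minimum power, recomputed | SAP Table 3.1-1 |
|---|---|---|---|
| -0.36 | 1.0 | 90.1% | 90.03% |
| -0.36 | 1.1 | 85.3% | 85.25% |
| -0.36 | 1.2 | 80.3% | 80.25% |
| -0.68 | 1.0 | 99.98% | 99.98% |
| -0.68 | 1.1 | 99.92% | 99.92% |
| -0.68 | 1.2 | 99.74% | 99.73% |

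The plan's figures reproduce. They do not if 0.36 is read as the asymptotic Emax (minimum 71.7% at SD 1.0), so the difference at 600 mg is evidently the intended meaning. The sample size does not rely on the omitted covariate.

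**Step 2: effect of adding the covariate.** Let R² be the share of residual variance that days since onset explains once the covariates already in the model are fitted. The documents give no value, so R² is an assumption and zero belongs in the range. The stated SD is treated as the residual SD of the present model. The new residual SD is SD × √(1 − R²). The equivalent total sample size is 400 / (1 − R²). The 95% half-width for one dose against placebo at SD 1.2 is 1.96 × 1.2 × √(2/100 × (1 − R²)).

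| Assumed R² | Fall in SE | Equivalent N | Half-width, SD 1.2 | Minimum power at -0.36, SD 1.0 / 1.1 / 1.2 |
|---|---|---|---|---|
| 0 | 0% | 400 | 0.333 | 90.1 / 85.3 / 80.3% |
| 0.01 | 0.5% | 404 | 0.331 | 90.3 / 85.6 / 80.6% |
| 0.02 | 1.0% | 408 | 0.329 | 90.5 / 85.8 / 80.9% |
| 0.05 | 2.5% | 421 | 0.324 | 91.2 / 86.7 / 81.8% |
| 0.10 | 5.1% | 444 | 0.316 | 92.3 / 88.1 / 83.4% |

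**Step 3: cost.** The present model leaves 400 − 4 arms − 6 covariate terms (load 1, risk 1, antibodies 1, region 3) = 390 residual degrees of freedom. A linear onset term uses one more.

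Missing onset dates are the larger risk. If a fraction m of patients dropped out of the model because the date is missing, the equivalent sample size would be 400 × (1 − m) / (1 − R²), which returns to 400 when m = R². At R² = 0.01, losing 4 patients cancels the gain; at 0.05, losing 20 does.

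**The case against.** The best defence is that this is a modelling preference. The SAP used the discretion that Protocol 12.4.2 gives it, added antibodies and region, and already adjusts the viral endpoint for its own baseline value. Another team could reasonably choose a different list. The analysis is valid as written and meets its power target. All of that stands.

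Four stronger readings are tempting, and the documents do not support them.

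- **That the SAP contradicts itself by using onset time in one model and not the other.** SAP 2.7.2.2 states that antibodies and region are in the Cox model, but says of onset time only that it will be evaluated. A symptom endpoint is also tied more directly to symptom timing than a viral one.
- **That precision is certainly being given up.** Baseline load and serology plausibly carry part of the same timing information. Eligibility narrows the range further: onset within 7 days and a positive antigen test on the dosing day. The remaining R² could be close to zero.
- **That Protocol Table 4-1 supports the covariate.** It expects "that in the first week after symptom onset the effect of ensovibep is most prominent". That concerns the size of the drug effect and helps explain the Day 8 endpoint. It does not show that onset day predicts outcome whatever the arm, and a main-effect term would not address effect modification.
- **That the change costs nothing.** No section names an onset-date field or says how complete it is; collection is inferred from the eligibility criterion and the Cox model. The date-imputation rules in SAP 5.1 do not cover symptom onset. Under its default handling, PROC MIXED would drop a patient whose onset date is missing.

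These points limit the size of the benefit and add a condition to the fix. They do not remove the case for pre-specifying a baseline value that the trial must establish at entry anyway.

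**Conclusion.** The omission is real and consistent across the primary, supportive and imputation models. It is not an error: it introduces no bias, and the power of at least 80% holds without the covariate. Adding it is an optional improvement whose benefit is unknown and probably small. At SD 1.2 and an effect of -0.36, it is worth about 0.3 power points if R² is 0.01, 1.5 if 0.05 and 3.1 if 0.10, and nothing if R² is zero. The figures assume that the stated SD is the residual SD of the present model, that a linear term is adequate, and that no patient is lost to a missing onset date.

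**What to change.** Before the Part A primary-analysis database lock and unblinding, amend SAP 2.5.2, 2.5.5 and 5.7.1 to include days from symptom onset to Day 1, as a continuous covariate, in the ANCOVA, the MMRM and the imputation models. In the same amendment, give a rule for missing onset dates that keeps every FAS patient in the model, for example imputing the overall median blind to treatment. It would also help to add the variable to the baseline characteristics in SAP 2.3.2. If the team prefers to leave it out, one sentence giving the reason would close the point.

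The cost is about one degree of freedom and a small programming change in three models. No protocol amendment or new data collection should be needed, provided that the onset date is recorded, as the eligibility criterion and the recovery model imply.
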